10.2. Baseline echocardiogram

If the qualifying echocardiogram study (TTE or resting images from a stress echo) was performed less than 6 months before randomisation, this study can also be submitted to the core lab to calculate baseline LVEF.

If the qualifying echocardiogram was done more than 6 months before randomisation, or the qualifying LVEF was assessed using MRI, a further transthoracic echocardiogram should be carried out soon after randomisation and this study submitted to the core lab to calculate baseline LVEF.

10.3. Qualifying EF flowchart:

10.4 Patients with recent MI

In the event of a recent myocardial infarction (clinical definition), assessment of qualifying LVEF should be based on a MRI or echocardiogram performed at least 4 weeks after the event.

When a completely new diagnosis is made of heart failure or ischaemic cardiomyopathy, it is recommended that the qualifying echocardiogram or MRI be performed after heart failure medication has been initiated.

10.5. Echo core lab

All trial echocardiograms should be performed in accordance with the minimum standard set out by the British Society of Echocardiography. Baseline, 6-month and 12-month echocardiograms will be anonymised and submitted to an independent echocardiography core laboratory (at Guy's and St Thomas' Hospital, London, UK), which will determine LV volumes and EF using a Simpson's biplane method, for evaluation of the major secondary outcome. The core laboratory will be blinded to treatment assignment as well as to the timing of the studies in relation to randomisation. Core laboratory analysis will also include the degree of mitral regurgitation and segmental wall motion.

In cases where endocardial definition is suboptimal, please consider using intravenous contrast to improve delineation.

Echo core lab analysis will include estimation of end diastolic and end systolic volumes, calculation of LVEF using the Simpson's biplane method and grading segmental wall motion.

10.6. Angiography core lab

Both pre-randomisation and trial procedure coronary angiogram and angioplasty images will be transferred to an angiography core laboratory (at Golden Jubilee National Hospital, Glasgow, UK) via anonymised optical media. Each participant's pre-randomisation BCIS-1 JS and PCI procedural success will be independently validated by the core laboratory. The core laboratory will calculate a number of other scores reflecting the anatomic complexity of coronary disease, the extent of effective revascularisation and the complexity of CTO lesions.

This data will be used to conduct a number of sub-analyses to identify predictors of benefit for the primary and secondary outcomes. The core laboratory will subsequently provide the relevant data to the Sponsor and CTU at the London School of Hygiene & Tropical Medicine for analysis against the data held in the eCRF.

11. Assessment of Viability

Eligibility for the trial will require demonstration of myocardial viability in at least 4 dysfunctional myocardial segments, subtended by diseased coronary arteries that can be treated by PCI.

Regional function at rest will be scored according to the American Heart Association 17 segment-5 grade scoring model (1: normal; 2: mildly hypokinetic; 3: severely hypokinetic; 4: akinetic; 5: dyskinetic)(43). Segments with resting wall motion abnormalities (grade 2-5) will be considered dysfunctional.

Segmental viability can be determined by any imaging modality. The criteria for determining viability will be based on local protocols and as determined by the local imaging specialist,

using all available information; the following are guidelines for defining segmental viability in the REVIVED trial:

- DSE: improvement in contraction by at least one wall motion grade during low-dose Dobutamine stimulation, compared to resting wall motion (improvement by at least 2 grades if aneurysmal or dyskinetic at rest).
- MRI: ≤25% transmural late gadolinium-enhanced (LGE) images. Adjudication of viability in segments with 26-50% transmurality will be at the discretion of the recruiting centres, on the basis of other available information, including of contractile reserve during low-dose Dobutamine stimulation.
- SPECT: tracer activity on the delayed images that is ≥50% of the activity in the segment with maximal activity (in rest-redistribution protocols).
- PET: perfusion metabolism (FDG) mismatch.

Imaging and intervention specialists at each participating centre will adjudicate segmental viability and the feasibility of revascularising the relevant segments, to determine whether an individual patient will be eligible for randomisation.

12. Randomisation

Potential patients will be reviewed by the Principal Investigator before randomisation with all available tests/notes to confirm eligibility.

Once the eligibility of a patient is confirmed by the trial coordinators and written informed consent obtained, randomisation will be carried out via an online web based system. Randomisation of the treatment assignment will be stratified by centre using randomly permuted blocks of varying size, with 1:1 allocation between the PCI and OMT arms.

There is no time limit from randomisation to PCI. However, it is recommended that index PCI be carried out as close as possible to randomisation to minimise the incidence of major adverse cardiovascular events (MACE) prior to the assigned treatment. Clinical events that occur after randomisation but before planned PCI will be attributed to the assigned treatment on an intention-to-treat basis.

13. Percutaneous Coronary Intervention

13.1. Adjunctive therapy and devices

PCI will be performed according to local protocols. Dual antiplatelet therapy should be given in all cases, with pre-loading, and the post-PCI duration based on the individual's bleeding risk and local/national guidelines. In general, drug-eluting stents are recommended, but in patients who have an indication for long-term formal anticoagulation (e.g. for concurrent atrial fibrillation, LV thrombus or venous thromboembolic disease), the choice of stent type should be based on their suitability for medium-term combined antiplatelet and anticoagulation therapy.

13.2. Completeness of Revascularisation

It is strongly recommended that PCI is considered and, if feasible, attempted on all significant coronary lesions in major proximal coronary vessels (or side branches >2.5mm in diameter) subtending viable myocardium. Lesion significance is defined as >70% diameter stenosis on angiography or for lesions between 50 and 70% diameter stenosis, when accompanied by

demonstrable reversible ischaemia on invasive or non-invasive testing. Planned target lesions will need to be identified by the operator and recorded by the trial coordinator before the procedure.

Patients who meet inclusion criteria and have CTO of coronary arteries subtending viable myocardial segments *should* be considered for REVIVED, provided that the PCI operators predict a high likelihood of successfully reopening these vessels. It is recommended that dedicated CTO operators, in units that have this degree of specialisation, undertake such cases.

The coronary disease burden at baseline and the degree of final revascularisation will be characterised by the BCIS-1 JS and Revascularisation Index (RI) (44), where $RI = (JS_{pre} - JS_{post})/JS_{pre}$.

13.3. Staged PCI

A single stage strategy should be employed where possible. However, provisional staging could be considered in patients with renal dysfunction, complex coronary disease (including chronic total occlusions) or if it is felt during PCI that deferring intervention to one or more vessels is in the patient's best interests (e.g. due to unexpected high contrast volumes or procedural complications during PCI to the first vessel). Staging must be pre-specified at the index procedure.

Urgent revascularisation before the planned 2nd stage procedure will be considered a major endpoint(45).

13.4. PCI Definitions

Target Vessel Success	<30% residual stenosis and Thrombolysis in Myocardial Infarction (TIMI) III flow in target vessel.
Procedural Success	Target vessel success in ALL treated vessels.
Major Procedural Complication	VT/VF requiring defibrillation. Cardiorespiratory arrest requiring assisted ventilation. Prolonged hypotension. (Prolonged hypotension = Mean arterial pressure ≤75 mmHg for >10 min despite fluid resuscitation or requirement of inotropic support / IABP / left ventricular assist device (LVAD) to maintain augmented mean arterial pressure >75 mmHg).
Major Bleeding	≥4 g/dL decrease in haemoglobin relative to baseline (if transfusion required, 1 unit of packed cells / whole blood considered equivalent to 1 g/dL drop in haemoglobin) or intra-cranial haemorrhage.
Minor Bleeding	2-4 g/dL decrease in haemoglobin relative to baseline.

Access complication	Haematoma/limb ischaemia requiring surgical or percutaneous intervention. Documented false aneurysm / arterial occlusion.
Acute Kidney Injury (AKI)	An increase in serum creatinine to >150% of the pre-PCI level, within 48 hours of PCI.

14. Optimal Medical Therapy

It is recommended that patients are **initiated** on medical therapy prior to randomisation, however the doses **do not necessarily need to have been optimised** before a patient can be randomised.

In order to ensure that patients in both arms of the trial receive optimal medical and device therapy, there is a nominated heart failure lead at each participating centre who is actively involved in patient selection and monitoring of therapy during the course of the trial. Furthermore a trial Medical Therapy Committee has been established, which will review available evidence and guidelines at least annually and refine recommendations to ensure that drug and device therapy given to all patients in the trial remains optimal and contemporary. Each site is provided with a standard operating procedure for delivering and monitoring OMT, which sets out classes of drugs appropriate for trial patients, including heart failure therapies (such as angiotensin-converting-enzyme (ACE) inhibitor or angiotensin receptor blocker +/- neprilysin inhibitor, betablocker and mineralocorticoid receptor antagonist(13)) and secondary prevention for atherosclerosis (including statin and antiplatelet agent) as well as recommended treatment targets (including lipid profile, HbA1c, resting heart rate). Formal anticoagulation for LV thrombus detected on imaging or as prophylaxis for severe LV dysfunction / dyskinesis is at the discretion of the treating physician. Initiation of the above treatments, dose-titration and relevant monitoring is per local heart failure protocols.

15. ICDs and Cardiac Resynchronisation

ICD implantation is not a requirement for inclusion in REVIVED.

Local guidelines should be followed when deciding on device therapy but the decision to implant (or not implant) a device should be made before randomisation. This plan will be documented in the CRF at baseline.

In evaluating whether an ICD should be implanted, physicians should assume that all patients would be assigned to OMT alone, to minimise the risk of trial outcomes being affected by treatment bias.

16. Data collection and follow-up

16.1. Tests required for eligibility

The following tests are required for identifying and screening patients. These are all standard of care tests and must be performed before patient consent:

- Demographics and medical history
- Coronary angiogram
- Viability assessments
- LVEF assessment in the case of patients with ACS, this must be done at least four weeks after the ACS
- Creatinine and electrolytes

16.1.1. Time limits for screening tests

Eligibility criteria	Test	Time limit
Extensive coronary disease	Angiogram	Clinically valid
LVEF ≤35%	Resting LVEF assessment	1 year prior to randomisation (at least 4 weeks after ACS)
Viability in at least 4 dysfunctional segments, that can be revascularised by PCI	Viability assessment	Clinically valid

16.2. Trial Checklist

	Tests required for eligibility	Baseline	Pre-PCI as per local protocol ‡	At discharge (up to 16 hours) post-PCI #	48 hrs post-PCI ‡	At 6 months post randomisation	At 1 year after randomisation	At 2 years after randomisation	Yearly follow-up	End of trial follow-up
Clinical assessme	nts (standa	ard of car	e)							_
Demographics and medical history	x									
Coro Angio	Х									
Viability assessment	х									
LVEF Assessment	Х*									
Echo		Χ [†]								
ICD check		Х				х	Х	х		
FBC	х			х						
Creatinine	х			х						
HbA1C		Х								
Full Lipid Profile		Х								
СК			Х	х						
Trop T/I		Х	Х	х		х	X			
ECG		Х		х						
AKI					X					
Trial specific asse	ssments		1	T		,		ı		ı
Echo						х	Х			
BNP / NT-proBNP		х				х	X	х		
NYHA/CCS		Х				х	X	х		
EQ-5D-5L		Х				х	X	х	Х	Х
KCCQ		Х				х	Х	х		
Primary Endpoint				x		x	x	х	х	х
Secondary Endpoints						х	Х	х	х	
SAEs				х		х	Х	Х		
Cardiac Medication ‡ If PCI is staged.		x		X		х	х	x		

[‡] If PCI is staged, please collect for each stage of the procedure

^{*} In the case of patients with Acute Coronary Syndrome (ACS), must be >4 weeks after ACS

[†] This echo is only required if there is no available echo within 6 months of randomisation and >4 weeks after ACS

Baseline (up to 6 months prior to randomisation):

- Echo
- Viability assessment report
- ICD check
- HbA1C
- Full lipid profile
- BNP / NT-proBNP
- ECG
- NYHA/CCS
- EuroQol EQ-5D-5L
- Kansas City Cardiomyopathy questionnaire (KCCQ)
- Cardiac medication
- Troponin T/I (OMT arm only)

Pre-PCI as per local protocol (If PCI is staged please collect for each stage of the procedure):

Troponin T/I or CK

At discharge (or up to 16 hours) post-PCI (If PCI is staged please collect for each stage of the procedure):

- Death
- Creatinine & Electrolytes
- Troponin T/I or CK
- ECG
- Unexpected serious adverse events
- Cardiac medication

48 hours after PCI (If PCI is staged please collect for each stage of the procedure):

AKI

6 months after randomisation (clinical follow-up):

- Death
- Hospitalisation due to heart failure
- MI
- Major bleeding
- Unplanned further revascularisation
- LVEF on echocardiography
- ICD check
- BNP / NT-proBNP
- NYHA/CCS
- EuroQol EQ-5D-5L
- Kansas City Cardiomyopathy questionnaire (KCCQ)
- Hospitalisation (at St Thomas' only)
- Unexpected serious adverse events
- Cardiac medication
- Troponin T/I

1 year after randomisation (clinical follow-up):

- Death
- Hospitalisation due to heart failure
- MI

- Major bleeding
- Unplanned further revascularisation
- LVEF on echocardiography
- ICD check
- BNP / NT-proBNP
- NYHA/CCS
- EuroQol EQ-5D-5L
- Kansas City Cardiomyopathy questionnaire (KCCQ)
- Hospitalisation (at St Thomas' only)
- Unexpected serious adverse events
- Cardiac medication
- Troponin T/I

2 years after randomisation (clinical follow-up):

- Death
- Hospitalisation due to heart failure
- MI
- Major bleeding
- Unplanned further revascularisation
- ICD check
- BNP / NT-proBNP
- NYHA/CCS
- EuroQol EQ-5D-5L
- Kansas City Cardiomyopathy Questionnaire (KCCQ)
- Hospitalisation (at St Thomas' only)
- Unexpected serious adverse events
- Cardiac medication

Years 3 to 8 after randomisation (telephone follow-up):

- Death
- Hospitalisation due to heart failure
- MI
- Unplanned further revascularisation
- Hospitalisation (at St Thomas' only)
- EuroQol EQ-5D-5L

Final follow-up at end of trial (telephone follow-up):

- Death
- Hospitalisation due to heart failure
- EuroQol EQ-5D-5L

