4.3. Other Secondary Endpoints

Cardiovascular death
All-cause death
Hospitalisation due to heart failure
Acute myocardial infarction (MI)
Appropriate implantable cardioverter defibrillator (ICD) therapy
Unplanned further revascularisation
Canadian Cardiovascular Society (CCS) angina class
Health resource use
Serial Troponin (T or I) levels
Serial brain natriuretic peptide (BNP or NT-proBNP) levels
Major bleeding

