16.3.4. Mortality Tracking

In addition to telephone and hospital follow-up, mortality tracking will be carried out via NHS Digital for up to 5 years from enrolment of the last patient.

17. Health Economic Analysis

A formal health economic analysis will be carried out under the leadership of [name], who heads the team for the Economic Evaluation of Health Technology Assessment at the Centre for Health Economics at the University of York, UK.

REVIVED-BCIS2 will provide a vehicle to collect data to support a cost-effectiveness analysis of PCI in heart failure. Data will be collected on NHS resource use including inpatient days in hospital, use of cardiovascular medication and devices and subsequent cardiovascular procedures. These data will be collected via record forms and questionnaires to patients.

In addition, data will be collected on health-related quality of life using the EQ-5D-5L instrument, a generic, preference-based measure. This will be administered at baseline, at 6-month follow-up and at annual intervals subsequently. Resource use will be valued in monetary terms using routine unit cost data relevant to the NHS. These will include NHS Reference Costs, British National Formulary drug prices and the Personal Social Services Research Unit (PSSRU) survey of unit costs.

In terms of analysis, the economic evaluation will consist of a description of resource use, costs and EQ-5D-5L data collected within the trial. A formal cost effectiveness of PCI in this population will be undertaken using a decision analytic framework which is necessary for two main reasons. Firstly, to extrapolate costs and benefits over a longer-term time horizon than that implied by the follow-up period of RCTs. For example, any impact of PCI on mortality will need to be expressed in terms of additional survival duration which requires a model to reflect long term all-cause mortality risks for this patient group. The second reason for using a modelling framework is that it provides a means of synthesising the evidence collected in REVIVED-BCIS2 with any other relevant evidence available in the literature. Most importantly

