11.1 Analysis Methods

11.1.1 Health Resource Consumption and Costs

Data on resource use will be collected for the entire duration of the trial for each participant. Costs will be calculated for each trial participant as the product of resource units used and the relevant unit cost.

The following types of resource use will be used for cost estimation: Cost of treatments undertaken (trial or non-trial treatments, e.g. IV diuretics). Costs of out-patient hospital visits and hospital in-patient stay Costs of events since discharge e.g. unplanned revascularisation Costs of cardiac medication e.g. statins Resource use information will be available from study data record forms (CRFs) for each patient. For each participant the relevant resource use information will include: Number of hospital admissions without overnight stays due to HF or other reasons Number of nights in hospital for in-patient stay due to HF or other reasons The type and number of trial treatments The type and number of non-trial treatments, including medication The year of pricing will be of 2021. Unit costs associated with resource use in each treatment arm will be estimated based on the appropriate version of NHS reference costs database and Personal and Social Services Research database. Unit costs of REVIVED SAP

treatment products will be obtained from the appropriate edition of British National Formulary (BNF). In case the information is not available in the BNF database, product costs will be obtained from the manufacturer.

The results section will summarise the costs by type of resource consumed for the two treatment arms. Descriptive statistics for total costs will also be summarised by trial arm at baseline, 6 months, yearly and end of trial follow-up.

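### The visit lists ask for all-cause hospitalisation at one centre only, while the economic analysis needs in-patient stays for any cause from every participant

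*Protocol*

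**What the plan says.** Protocol section 4.3 lists "Health resource use" among the other secondary endpoints, with no restriction to a subset of centres.

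Protocol section 16.2 gives a list of items for each contact. The 6-month, 1-year, 2-year and years 3 to 8 lists each contain "Hospitalisation (at St Thomas' only"). The same lists contain "Hospitalisation due to heart failure", MI and "Unplanned further revascularisation" with no centre named. The final telephone contact lists death, heart failure hospitalisation and EQ-5D-5L only. The checklist tables in section 16.2 and in SAP Appendix 3 have no row for hospital admissions.

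Protocol section 17 states: "Data will be collected on NHS resource use including inpatient days in hospital, use of cardiovascular medication and devices and subsequent cardiovascular procedures". It gives record forms and patient questionnaires as the route.

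SAP section 11.1.1 states: "Data on resource use will be collected for the entire duration of the trial for each participant". Among the inputs to be costed it names "Number of nights in hospital for in-patient stay due to HF or other reasons", and it gives the CRFs as the source for each patient. The SAP's within-trial outline sets the period of analysis at 8 years.

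**The concern.** A site that works from the section 16.2 lists, and is not the named centre, has no scheduled item under which to record an admission for a cause other than the listed events. A non-cardiac stay is the plain example. Yet the economic analysis counts such stays for every participant over the whole trial.

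Two things are at stake. The endpoint of health resource use, and the NHS-perspective cost built on it, would leave out part of in-patient use at most centres. And if PCI and OMT differ in other-cause admissions, the cost comparison could not show it. Nothing in the documents explains why the item is tied to one centre, so a site cannot tell whether the restriction is deliberate.

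**Working it through.** The plan gives no figure to reproduce here. The check is a comparison of sections, plus one calculation of how many patients are outside the named centre.

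**What the economic plan needs.** In-patient days without limit by centre or cause (protocol section 17); nights for any reason, each participant, entire trial, from CRFs (SAP section 11.1.1).

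**What is scheduled at all centres.**
- Heart failure hospitalisation: every follow-up list and the final contact (section 16.2).
- MI and unplanned revascularisation: every list through years 3 to 8 (section 16.2). SAP section 9.3 plans summaries of details of these events, with days in hospital among its examples.
- The PCI stay: days in hospital are recorded (SAP section 7.6).
- Major bleeding and unexpected SAEs: to 2 years (section 16.2).
- ICD or CRT implantation after randomisation: date, to 2 years (SAP section 9.6.2).

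**What is scheduled at one centre only.** Hospitalisation in general, at 6 months, 1 year, 2 years and years 3 to 8. At the final contact it is scheduled nowhere.

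**Could another source in the documents fill the gap?**
- *Questionnaires.* The only ones scheduled are EQ-5D-5L and KCCQ, and neither measures resource use.
- *SAE reports.* Scheduled only to year 2. Section 5.1 confines them to unexpected events that are neither endpoints nor expected PCI complications. No section says that they capture nights in hospital.
- *Record linkage.* The NHS Digital tracking in section 16.3.4 is for mortality. No linkage for admissions is described.

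What remains is admissions for other causes outside the named centre. To year 2, some of these would surface as SAEs or as device dates. In years 3 to 8 neither route is scheduled, so the gap is widest there.

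**Share of patients.** Inputs: 700 patients and 35 to 40 centres (protocol section 1.1). Recruitment at the named centre is not stated, so it has to be assumed.
- Equal recruitment, 40 centres: 700/40 = 17.5 patients; 17.5/700 = 2.5%; outside the centre 97.5%.
- Equal recruitment, 35 centres: 700/35 = 20 patients; 20/700 = 2.9%; outside the centre 97.1%.
- Named centre at an assumed 5%: 0.05 × 700 = 35 patients; 665/700 = 95% outside.
- Named centre at an assumed 20%: 0.20 × 700 = 140 patients; 560/700 = 80% outside.

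Under each assumption a large majority of patients is outside the item.

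**The case against.** The strongest reply is that the lists are not the forms. The SAP says that CRF version 6 was reviewed in preparing it, and it states that resource-use information, including nights for reasons other than heart failure, will be available from CRFs for each patient. Section 17 adds patient questionnaires as a route. The checklist table also has a row for secondary endpoints at 6 months, 1 year, 2 years and yearly, and health resource use is one of them. This stands to the extent that the documents show a conflict, not an absence of data. A reader might infer that the data cannot exist; the forms are not shown, so that does not follow.

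A reader might also infer that all in-patient data other than heart failure are missing outside the named centre. The documents do not support that, given the trial-wide items set out above. Device implantation is a poor example of a complete loss, because its date is collected at all centres to year 2.

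Nor do the documents support a claim that almost every patient is affected, since that depends on a recruitment figure they do not give.

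Finally, randomisation is stratified by centre, so the restriction applies to both arms alike. That is correct, and the documents give no evidence that other-cause admissions differ between arms. But stratification balances who lacks the item. It does not recover admissions that go unrecorded, nor a difference between arms in their number or length.

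**Conclusion.** The point holds as an unresolved contradiction between protocol section 16.2 on one side and protocol section 17 with SAP section 11.1.1 on the other. Followed as written, the lists leave other-cause admissions unscheduled at all centres but one, and unscheduled everywhere at the final contact.

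The size is a large majority of patients: about 97% if centres recruit equally, and 80% to 95% if the named centre recruited 5% to 20%. Both are assumptions.

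If the restriction is real, total in-patient cost is understated in both arms, and any PCI versus OMT difference in other-cause admissions is missed. If it is a drafting remnant, the lists leave out data that the analysis requires. The primary endpoint and its power are not affected.

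**What to change.** Reconcile section 16.2 with section 17 and SAP section 11.1.1, in one of two ways.

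1. Remove the one-centre restriction. Record all-cause admissions (date, nights, main reason) at every centre at the contacts already planned, including the final one. Add a matching row to the checklist tables in section 16.2 and SAP Appendix 3. The cost is a protocol and eCRF amendment and a little more site data entry, with no new visit or test. Contacts that have already taken place may need retrospective entry.

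2. If that is not done, state in section 17 and SAP section 11.1.1 that in-patient costs cover only the event types collected trial-wide, and do not present them as total NHS resource use. This needs only a change of text and remains possible late in follow-up. The price is a narrower cost comparison.
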